9.9.1.2. Hematocrit

At the baseline visit, study staff will draw blood into a 2 ml EDTA tube to assess the participant's hematocrit. Study staff will then draw blood from the EDTA tube into a capillary tube, seal the capillary tube, and centrifuge it in a Gemmyco KHT-410E Micro centrifuge for five minutes at the preset fixed speed of 12,000 rpm. Hematocrit will be assessed using a measuring device that will determine the ratio of the volume of red blood cells to the total volume of blood.

9.9.1.3. HIV-1 RNA (viral load)

At all five study visits, study staff will additionally draw blood into a 5mL EDTA (purple top) or anticoagulated PPT (white top) tube to assess patient plasma viral load at the end of the study. After collection, the primary tubes of EDTA/PPT blood samples will be centrifuged at 3500rpm for 10 minutes to separate plasma from cells. The plasma will be removed carefully into cryovials which will be transferred to J52 Groote Schuur for storage at -80°C within 24 hours of collection. HIV-1 RNA level will be determined by HIV VL assay performed at HLS laboratories using Alinity m HIV-1 assay (Abbott Laboratories, Abbott Park, USA).

Plasma VL samples will be analyzed in a batch when the participant completes the study. Viral load information will not be shared in real-time as it would undermine the ability to evaluate the impact of DBS results feedback. This study does not affect any standard of care viral load monitoring which occurs in South Africa on an annual basis. Once all viral load data are batch analyzed, we will share any raised viral load result (VL>50 copies/ml) with a participant's provider.

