9.5. Clinic Chart Review (Visits 1-4 and Post Study)

Study staff will review participants' clinic charts at all visits and post-study to determine if any changes to medical or adherence management were made by providers since the previous visit. These changes could include: additional VL requests (beyond those prescribed for a stable patient), referral for intensive counsellor-based or group adherence counselling (usually only accessed if VL flagged as raised), outreach by Community Care Workers (CCWs) for adherence monitoring and support; and additional doctor-requested patient appointments. To mitigate the risk of control group participants receiving interventional DBS feedback, providers will not receive DBS results for participants in the control group.

The expected quality of the notes in the clinical charts will be variable with some clinicians making detailed notes and others making less detailed notes. The study team is reviewing FDW feedback and considering the creation of a checklist to facilitate identifying and quantifying actions that a provider may take based on DBS results .

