9.6. Provider Focus Group Discussions

Once all pilot participants have completed their final visit (visit 4), study staff will hold the provider FGD to ascertain their understanding and perception of the utility of the DBS feedback and what changes they made (if any) in managing the participant's care and what additional communication (if any) they initiated with the participant. Closer to the end of the Aim 2 study, a focus group guide will be developed prompting providers to comment on whether the initial training prepared them to provide these results, whether they needed additional training, experiences they had during the study trial, and to describe any other thoughts or opinions that could inform feasibility and future scale-up of DBS feedback efforts in clinical settings. As this FGD might be scheduled out a month or two following the end of the study trial, providers will be given a window of 6-8 months for study participation.

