10. ASSESSMENT OF SAFETY

10.1 Safety Assessment Overview

As this study involves low-risk activities and does not involve the introduction of a drug or a drug change, standard adverse event reporting will not be undertaken. While the study is providing additional VL testing, these will not be run in real-time and are collected in a research capacity. Any VL above the 50 copies/ML will be shared after a participant completes the study. The study team will collect and report all social impacts that are brought to the attention of study staff members. Study staff will be trained to recognize and report social impacts as well as provided participants with referrals for counseling and social service support, if necessary. Reports of social impacts will be reviewed quarterly or more often, if indicated, and reported to the study Medical Officers together with any actions that are taken. Social impacts will be summarized and reported to appropriate IRBs and the Performance and Safety Monitoring Board (PSMB) on an annual basis.

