Because feedback begins at the first return visit at Month 1 after baseline, each Feedback Group participant will provide up to three change score outcomes (for month $i-1$ to month i for $i=2,3,4$). We will compare these to the corresponding change scores in the Control Group in a generalized linear model (GLM) using generalized estimating equations (GEE) to account for within-subject correlation (ICC) among their three change-scores. The analysis model will include a constant term and the group indicator.

With the limited pilot sample size of 60, we will be able to detect moderately large effects on average improvement in adherence. For example, if the ICC between successive change scores is no greater than 0.20, then the detectable standardized mean difference will be $2.8 * [(2/30) * (1 + 0.2 * (3-1))]^{1/2} = 0.86$, a "large" effect.

Given that this is a pilot study, our ability to explore the role of the moderating variables on adherence-related behavior will be limited. However, looking at the monthly change-scores can reveal important features on which to focus. Moreover, the larger Aim 1 sample (N=250) will provide key data on individual and structural factors affecting adherence, retention, and preferences for sample collection and feedback that we will utilize in multivariable analyses as predictors of DBS TFV-DP levels and Wisepill use patterns. We will also examine these factors as potential effect modifiers in Aim 1 analyses.

For providers we will examine changes in clinical management patterns, for example requests for additional tests or adherence counselling sessions usually only triggered by a raised VL.

Similar to Aim 1, the Baseline and Visit 4 (last visit) Quantitative Assessments will cover a large array of participant information and behaviors that could be potential confounders. To examine how potential confounding factors can influence our statistical analysis, we will first identify a list of variables that is possible be candidates for potential confounding factors and then test whether any of those variables is associated with our outcome (i.e., adherence) and exposure (i.e., the intervention) in our sample. If found, we will include them in the primary analysis model to obtain the adjusted intervention effect. While the official primary analysis will be the one without covariate adjustment, the adjusted analysis will help to interpret the findings from primary analysis.

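### Raised research viral loads go to providers in both arms after completion, and nothing keeps the actions they prompt out of the post-study chart review

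*Combined protocol and SAP*

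**What the plan says.** Research VLs are drawn at all five visits and withheld during follow-up. Section 9.9.1.3 gives the reason: "Viral load information will not be shared in real-time as it would undermine the ability to evaluate the impact of DBS results feedback". The withholding then ends. The same section says "Once all viral load data are batch analyzed, we will share any raised viral load result (VL>50 copies/ml", the recipient being the participant's provider. Section 10.1 agrees: "Any VL above the 50 copies/ML will be shared after a participant completes the study". Neither section limits the release to one arm.

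Provider behaviour is followed by chart review in both arms (section 4). Under section 9.5, staff review "clinic charts at all visits and post-study to determine if any changes to medical or adherence management were made by providers" since the previous visit. Table 1 marks this review at Months 1 to 4 and in the Post-Study column. One listed action is referral for adherence counselling, described as "usually only accessed if VL flagged as raised". Section 12.1 gives as examples of the provider outcome "requests for additional tests or adherence counselling sessions usually only triggered by a raised VL".

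The only contamination safeguard in section 9.5 concerns TFV-DP (DBS) results: providers do not receive them for control participants.

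**The concern.** The plan recognises that VL information in providers' hands would confound the evaluation of drug-level feedback. It protects against this up to completion, but one outcome interval opens at Visit 4. In that interval a raised research VL can reach providers in either arm and can prompt the actions being looked for. Table 1 schedules no TFV-DP feedback after Month 3, so any newly released VL arrives when no new drug-level result is scheduled.

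Clinical management of patients is part of primary objective (b) (section 6.1), and section 12.1 intends the pilot's estimates to inform a larger trial. An action prompted by a released VL could be read as a response to feedback in one arm and as usual care in the other. Section 9.5 expects notes of uneven quality, with "some clinicians making detailed notes and others making less detailed notes", and an action checklist is only under consideration. The chart alone may therefore not show what prompted an action.

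**Working it through.** The plan gives no rate, model or power for provider management, so there is no figure to reproduce. Its detectable difference of 5.59 points (section 12.1) concerns patient adherence and does not bear on this point.

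**Sequence of events**

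1. Last scheduled TFV-DP feedback: Month 3 (Table 1). The Visit 4 chart review covers the month after it.
2. Reviews at Visits 1-4 precede release of that participant's own research VLs, so those VLs cannot affect them.
3. VL batch: when the participant completes (9.9.1.3; likewise 9.2, section 13 and 10.1). The first sentence of 9.9.1.3, and 13.3.1, say the end of the study, which could mean later.
4. Post-study chart review: changes since Visit 4, undated.
5. Provider focus groups: "Once all pilot participants have completed their final visit (visit 4), study staff will hold the provider FGD".

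Steps 3 and 4 can therefore fall in either order. After first feedback there are four review intervals (months 1-2, 2-3, 3-4, and 4 to post-study). Only the last is exposed.

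**How many releases**

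Section 8.1.1 expects about 80% to be suppressed on the last standard-of-care VL. Taking the remaining 20% as the share with a raised research VL:

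- per arm: 0.20 × 30 = 6; both arms: 12 of 60
- at 10%: 3 per arm; at 30%: 9 per arm
- chance of at least one release in an arm at 20%: 1 − 0.8^30 = 99.9%

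The 20% describes status at entry. The share with any of five research VLs above 50 copies/mL could be higher.

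**Direction**

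Let p be the proportion with a provider action without the release, q the proportion with a raised VL released, and r the chance that a release prompts an action. If these act independently, the observed proportion in an arm is 1 − (1 − p)(1 − qr).

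- Equal q and r in both arms: observed difference = (p_F − p_C) × (1 − qr). With q = 0.20, r = 0.5 gives a factor of 0.90 and r = 1 gives 0.80. The arms move together.
- Lower q under feedback: control gains more actions. Assume p_F = 0.30, p_C = 0.05 and r = 1, a true difference of 25 points. With q = 0.20 in both arms the result is 0.44 − 0.24 = 20 points. With q_F = 0.10 and q_C = 0.20 it is 0.37 − 0.24 = 13 points.

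**Sensitivity to assumptions**

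Suppose instead that all actions fall among the 20% with a raised VL, and that before release 80% of them have an action under feedback and 10% under control. The difference is 0.16 − 0.02 = 14 points. If the release prompts action in half of those without one, it is 0.18 − 0.11 = 7 points; if in all, 0.20 − 0.20 = 0.

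The values of p, r and the unequal q are assumptions with no source in the documents. The formulas also presume one pooled any-action proportion per arm, which the plan does not specify. They show direction and how widely the size could vary; they do not estimate it.

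**The case against.** The strongest reply is that the overlap is possible but not established. A post-study review done soon after Visit 4, before results return, would be clean, and the end-of-study wording could push the release later still. That stands: a reader might infer that the review will count VL-prompted actions, but the documents leave the order open. What remains is that nothing requires the clean order, and most of the timing statements are per participant.

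A reader might also infer that the whole provider comparison, or the primary endpoint, is compromised. The documents do not support this. The Visit 1-4 reviews are unaffected by the participant's own research VLs, and because each review covers a defined interval, the last one can be set aside. Section 12.1 says only that changes in management patterns will be examined. Chart review is not among the measures listed in section 12.2.1. The focus groups are listed, but they are qualitative, ask about the use of the feedback, and yield no count by arm; providers can say what prompted a change.

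A further reply is that the 20% comes from routine VLs already in care. Patients who are persistently unsuppressed may already have been flagged, so the release may add little for them. This is fair and is another reason not to attach a size.

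Finally, section 14.3.1 lists disclosure of control-arm DBS results to providers as an optional, undated activity. VL may therefore not be the only information reaching control providers late.

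**Conclusion.** The point holds in limited form. As written, the plan allows raised research VLs to reach providers in both arms during the one interval that the post-study chart review covers. It neither orders the two events nor separates the triggers. The likely effect is dilution of any provider difference if raised-VL rates are similar, and greater distortion against feedback if feedback lowers VL as hypothesised in section 5.3. About 6 participants per arm would have a release if about 20% are unsuppressed. The effect on the comparison cannot be estimated, because action rates and the response to a released VL are not in the documents. Exposure is confined to one descriptive interval of a pilot, so this is a cheap improvement and not a threat to the trial's main results.

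**What to change.** In sections 9.5 and 12.1:

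1. Record the date of each provider action and the date on which each participant's raised VLs are released.
2. Limit the between-arm comparison of provider management to actions dated before that release, or up to Visit 4.
3. Report later actions separately, by arm, as possibly VL-prompted.

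Visit 4 is the simpler cut-off. A participant with no raised VL has no release date, so a release-based cut-off needs a stand-in for them, such as the date their batch results returned. Otherwise the length of the window would depend on VL and could differ by arm.

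Do not delay the release. Holding known raised results to protect one descriptive interval would be a poor trade, and the date rule makes it unnecessary.

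The cost is two extra dates per chart for 60 charts and a shorter post-study window for the comparison. No visits, blood draws or assays are added.

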9.9.1.4. Creatinine

Standard of care creatinine tests will be abstracted as part of this study. As the creatinine test is a component of the South Africa ART National programme, a value within the past 12 months should be available. Creatinine will be abstracted in order to estimate glomerular filtration rate (eGFR) which recent data has shown has implications on TDF-DP DBS drug concentrations.²⁴

9.9.2. Biohazard containment

As the transmission of HIV and other blood-borne pathogens can occur through contact with contaminated needles, blood, and blood products, appropriate blood and secretion precautions will be employed by all personnel in the drawing of blood and shipping and handling of all specimens for this study, as currently recommended by the Centers for Disease Control and Prevention in the United States, the WHO internationally and the National Institutes of Health.

Table 1: Schedule of events

Visit	Pre-Study	Screening at clinic	Baseline Month 0	Month 1	Month 2	Month 3	Month 4	Post-Study
Provider Consenting	X							
Provider Training- DBS Results and Interpretation	X							
Screening permission form		X						
Eligibility determination (age, ART regimen, time on ART)		X						
Medical Chart Confirmation (age, ART regimen, time on ART)		X						
Informed consent for eligible patients			X					
Locator form		X	X	X	X	X	X	
Height			X					
Weight			X	X	X	X	X	
Pregnancy Status			X	X	X	X	X	
Blood draw for hematocrit			X					
Medical chart review for past 12 month (Creatinine)			X					
Blood draw for HIV viral load (to be assayed at study completion)			X	X	X	X	X	
Blood draw for DBS			X	X	X	X	X	
Baseline Quantitative Assessment			X					
Self-Reported ART Adherence Questionnaire			X	X	X	X	X	
Dispense Wisepill device			X					
Wisepill Functionality Test				X	X	X		
Dispense patient reimbursement			X	X	X	X	X	
FEEDBACK ARM only: drug concentration feedback to patients and providers.				X	X	X		
Clinic Chart Review				X	X	X	X	X
Return Wisepill device							X	
Visit 4 Quantitative Assessment							X	
Provider FDGs								X

10. ASSESSMENT OF SAFETY

10.1 Safety Assessment Overview

As this study involves low-risk activities and does not involve the introduction of a drug or a drug change, standard adverse event reporting will not be undertaken. While the study is providing additional VL testing, these will not be run in real-time and are collected in a research capacity. Any VL above the 50 copies/ML will be shared after a participant completes the study. The study team will collect and report all social impacts that are brought to the attention of study staff members. Study staff will be trained to recognize and report social impacts as well as provided participants with referrals for counseling and social service support, if necessary. Reports of social impacts will be reviewed quarterly or more often, if indicated, and reported to the study Medical Officers together with any actions that are taken. Social impacts will be summarized and reported to appropriate IRBs and the Performance and Safety Monitoring Board (PSMB) on an annual basis.

10.2 Adverse Event Procedures and Reporting Requirements

DAIDS policy on Critical Events will be followed in the event of an unanticipated problem/s or other Critical Events.

11. CLINICAL MANAGEMENT

11.1 Clinical Management of Study-Related Adverse Events

Adverse events related to blood draw (bleeding, bruising, dizziness) will be managed on-site by the study staff. First Aid equipment is available. See standard Operating Procedure (SOP) C002 BLOOD SPECIMEN ACQUISITION, PROCESSING AND STORAGE GUGULETHU RESEARCH OFFICES (GRO).

All patients presented with an antiretroviral therapy-related adverse event will be referred to their ART clinic for management as these will not be related to our exploratory pilot study, as we will not be altering the participants ART regimen.

11.2 Other Disease Events

Not applicable.

11.3 Pregnancy

Not applicable.

11.4 Breastfeeding/Replacement Feeding

Not applicable.

11.5 Acquisition of HIV infection while on Study

Not applicable.

11.6 Treatment Failure

Not applicable; there is no experimental treatment.

11.7 Criteria for Discontinuation

11.7.1 Criteria for permanent intervention discontinuation for an individual participant.

The criteria for permanent intervention discontinuation from the study for an individual participant are:

- Request by participant to withdraw;
- Request of the provider if s/he thinks the study is no longer in the best interest of the participant;
- Provider changes participant's ART medication to one that does not contain tenofovir or requires participant to discontinue ART medication entirely; or
- Judgment by the investigator that the participant is at sufficient risk of failing to comply with the provisions of the protocol so as to cause harm to her/himself or seriously interfere with the validity of study results.

Participants who experience viral breakthrough *will not* be discontinued from the study. We will follow all study participants for the full follow-up period of 4 months barring safety concerns (including those who experience viral breakthrough), and will continue to collect blood samples and all other study data (i.e. assessments, Wisepill).

11.7.2. Criteria for premature study discontinuation for an individual participant.

The criteria for premature discontinuation from the study for an individual participant are

- Request by participant to withdraw;
- Request of the provider if s/he thinks the study is no longer in the best interest of the participant;
- Provider changes participant's ART medication to one that does not contain tenofovir or requires participant to discontinue ART medication entirely; or

- Judgment by the investigator that the participant is at sufficient risk of failing to comply with the provisions of the protocol so as to cause harm to her/himself or seriously interfere with the validity of study results.

In addition, participants who experience viral breakthrough *will not* be discontinued from the study. We will follow all study participants for the full follow-up period of 4 months barring safety concerns (including those who experience viral breakthrough), and will continue to collect blood samples and all other study data (i.e. assessments, Wisepill).

12. STATISTICAL CONSIDERATIONS

12.1. Overview and General Design Issues

For Aim 2, we will explore whether providing adherence feedback to patients and providers results in changes to patient adherence behavior (as measured by TFV-DP levels, VL, Wisepill use patterns, and self-report) and/or provider behavior with respect to patient management (e.g., requests for additional laboratory tests, calling patient back for an additional appointment, referring patient to an adherence counselor, referring patient to the 'risk of treatment failure clinic'). Below we describe the analytical plan to assess change in patient adherence behavior using Wisepill openings as an example.

This 5-month pilot with a small sample size, will provide preliminary estimates that can be used to inform future power calculations and the design of a larger trial (e.g., estimates of effect size, interclass correlation [ICC] for within individual and within provider/clinic correlation). Using Aim 1 data on self-reported adherence, which includes about 3,000 observations, the mean adherence is 81.96% with a standard deviation of 11.42%. The current plan to recruit 60 subjects and collect their monthly adherence data over the subsequent 4-month period will result in 180 change scores (90 per group) for the Aim 2 analysis. Using the estimated standard deviation from our existing data and assuming the ICC between successive change scores is no greater than 0.20, we will be able to detect a 5.59 percentage point difference in ART adherence between the intervention and control group with 80% power. Assume the mean adherence is about 80% for the control group (very close to what we observed from our observational study in Aim 1), if in truth, the mean adherence is 85.59% (which we optimistically believe is achievable), we have 80% probability to declare the difference of adherence between intervention and control is statistically significant. Therefore, we believe that the data we will collect from 60 participants over the 4-months of follow up will provide adequate power to achieve the study goal.

To generate preliminary estimates of the effect of giving feedback on adherence behavior, we will compare change in average percentage of Wisepill openings (for example) from one month to the next between Feedback and No Feedback (Control) participants.

Because feedback begins at the first return visit at Month 1 after baseline, each Feedback Group participant will provide up to three change score outcomes (for month $i-1$ to month i for $i=2,3,4$). We will compare these to the corresponding change scores in the Control Group in a generalized linear model (GLM) using generalized estimating equations (GEE) to account for within-subject correlation (ICC) among their three change-scores. The analysis model will include a constant term and the group indicator.

With the limited pilot sample size of 60, we will be able to detect moderately large effects on average improvement in adherence. For example, if the ICC between successive change scores is no greater than 0.20, then the detectable standardized mean difference will be $2.8 * [(2/30) * (1 + 0.2 * (3-1))]^{1/2} = 0.86$, a "large" effect.

Given that this is a pilot study, our ability to explore the role of the moderating variables on adherence-related behavior will be limited. However, looking at the monthly change-scores can reveal important features on which to focus. Moreover, the larger Aim 1 sample (N=250) will provide key data on individual and structural factors affecting adherence, retention, and preferences for sample collection and feedback that we will utilize in multivariable analyses as predictors of DBS TFV-DP levels and Wisepill use patterns. We will also examine these factors as potential effect modifiers in Aim 1 analyses.

For providers we will examine changes in clinical management patterns, for example requests for additional tests or adherence counselling sessions usually only triggered by a raised VL.

Similar to Aim 1, the Baseline and Visit 4 (last visit) Quantitative Assessments will cover a large array of participant information and behaviors that could be potential confounders. To examine how potential confounding factors can influence our statistical analysis, we will first identify a list of variables that is possible be candidates for potential confounding factors and then test whether any of those variables is associated with our outcome (i.e., adherence) and exposure (i.e., the intervention) in our sample. If found, we will include them in the primary analysis model to obtain the adjusted intervention effect. While the official primary analysis will be the one without covariate adjustment, the adjusted analysis will help to interpret the findings from primary analysis.

An exploratory content analysis will be used to identify themes in the open-ended segments of the exit interview and the FGD discussion. These analyses will focus on themes related to training, process of providing results, and the strengths and challenges of using DBS-based feedback in the clinic setting.

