12.6. Participant Enrollment and Follow-Up

The study will recruit 60 HIV-positive patients who are taking ART containing tenofovir in the past 4 months. We expect to recruit an average of 15-20 participants/month for 4 months and suffer no more than 10% dropout.

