12.7.1.2. Monitoring retention performance

For monitoring purposes, a "dropout" will be operationalized as a participant having missed two or more consecutive scheduled visits. A visit will be considered "missed" once 2 weeks have passed since the target visit date. We acknowledge that a participant who is deemed a dropout may subsequently return to the study. If at any time the percent of all enrolled participants who are current dropouts exceeds 15%, the PSMB will review and identify retention problems and recommend appropriate remedies.

12.7.2 Analysis plan.

Not applicable for this pilot trial.

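### The 80% power for 5.59 points assumes all 180 change scores; at the 10% dropout the plan allows, the calculation that reproduces 5.59 gives about 75–77%

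*Combined protocol and SAP*

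**What the plan says.** Section 12.1 plans for 60 participants and states that their monthly data "will result in 180 change scores (90 per group) for the Aim 2 analysis". The inputs are an Aim 1 summary of self-reported adherence, in which "the mean adherence is 81.96% with a standard deviation of 11.42" percent, and a correlation set by "assuming the ICC between successive change scores is no greater than 0.20". From these it concludes that "we will be able to detect a 5.59 percentage point difference in ART adherence between the intervention and control group with 80% power", and that 60 participants are adequate for the study goal.

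Later in 12.1, the analysis description says that "each Feedback Group participant will provide up to three change score outcomes", one for each of the month pairs 1–2, 2–3 and 3–4. That text also prints a detectable standardized difference of 0.86, computed with 2/30 under the root.

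Section 12.6 keeps recruitment at 60 and expects to "suffer no more than 10% dropout". Section 12.7.1.2 defines a dropout, for monitoring, as "a participant having missed two or more consecutive scheduled visits".

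**The concern.** Since 60 × 3 = 180, the power statement uses the maximum possible number of scores. It leaves no room for the loss that section 12.6 allows, and no section inflates the 60 or gives power for fewer scores.

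For a measure taken at visits, each change score needs two adjacent visits. Someone who misses two consecutive visits therefore keeps at most one of the three scores. Missing visits 3 and 4 leaves months 1–2, missing 1 and 2 leaves months 3–4, and missing 2 and 3 leaves none.

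At stake is whether the 80% and the claim of adequacy hold under the plan's own retention ceiling. The pilot's estimates are also meant to inform the power calculation of a larger trial, and a template without a dropout allowance could be carried into it.

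**Working it through.** **Inputs.** From 12.1: SD 11.42 points, ICC 0.20, three scores per person, 30 per arm, difference 5.59. From 12.6: dropout up to 10%, which is 6 of 60, taken here as 3 per arm. The plan does not state alpha in words. I assume two-sided 5%, because the printed multiplier 2.8 equals 1.96 + 0.84.

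**Formula.** A person with m scores contributes m / [1 + 0.20(m − 1)] independent scores: 3/1.4 for a completer and 1 for someone with a single score. With I the sum per arm, SE = 11.42 × √(2/I), power = Φ(5.59/SE − 1.96), and the difference detectable with 80% power = 2.8016 × SE.

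**The plan's own figure.** With all 60 complete, I = 90/1.4 = 64.29 and SE = 2.014. Power is Φ(0.815) = 79.3% and the detectable difference is 5.64. That matches the stated 80% and 5.59 closely, though not exactly. One-sided 5% would give 87.1% and a first-order autoregressive correlation 82.3%, so neither fits as well.

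**With 10% dropout.**

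| Case | Scores in total | I per arm | SE | Power at 5.59 | Detectable at 80% |
|---|---|---|---|---|---|
| No loss | 180 | 64.29 | 2.014 | 79.3% | 5.64 |
| Each dropout gives one score | 168 | 27 × 3/1.4 + 3 = 60.86 | 2.070 | 77.0% | 5.80 |
| Dropouts give none | 162 | 81/1.4 = 57.86 | 2.123 | 74.9% | 5.95 |

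A mix of the three dropout patterns falls between the last two rows. If dropout were 5% with no scores from dropouts (28.5 per arm), power would be 77.2%.

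**The formula printed in 12.1.** It uses 2/30 and does not divide by the three scores: 2.8 × √[(2/30) × 1.4] = 0.855, printed as 0.86. At SD 11.42 that is about 9.8 points, not 5.59. With 27 per arm it becomes 2.8 × √[(2/27) × 1.4] = 0.902, or about 10.3 points. Taken literally, it gives about 36% power for 5.59 points with 60 completers and about 33% with 54.

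**What is common to both.** If dropouts give no scores, the detectable difference grows by √(30/27) = 1.054, about 5%, whichever formula is kept.

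**The case against.** The strongest reply is that Wisepill is the measure named in the objectives and in the analysis example. Section 9.8 has the device record openings continuously and store them for up to a year if the connection fails. A person who misses two visits but keeps using the box could still supply all three Wisepill scores. This stands: the loss described here applies to self-report, TFV-DP and viral load, and to Wisepill only once the device is out of use. It does not remove the point, because the SD behind 5.59 comes from self-report, which is collected at visits.

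Second, 75% is the unfavourable corner. It takes the full 10%, no scores from any dropout, and the ICC at its ceiling. With 162 scores, power would be 78.0% at ICC 0.15 and 81.2% at ICC 0.10. That is fair, and is why a range is given. But the plan's own 80% is also computed at ICC 0.20, so the like-for-like comparison is 79.3% against 75–77%.

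Third, the plan is a pilot and hedges: scores are described as up to three per person, and only fairly large effects are said to be detectable. This limits the importance, but the paragraph containing the 80% claim carries no such hedge.

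Two stronger readings are tempting. A reader might infer that power is 75% on the plan's own formula, whatever one thinks of that formula. The documents do not support this, because the only formula they print leads to about 36% and 33% for 5.59 points. A reader might also add further loss from isolated missed visits, for example 5% per visit. No such rate appears in the documents, and section 8.6 reports Aim 1 retention above 89% over 12 months, against 4 months of follow-up here.

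**Conclusion.** The power statement is wrong as written: 80% for 5.59 points is not delivered at the dropout ceiling the plan sets for itself. Under the 90-per-group calculation the shortfall is about 2 to 4 percentage points of power (79.3% to 77.0% or 74.9%), or a detectable difference of about 5.8 to 5.95 points instead of 5.64. This is a modest effect and changes no design decision.

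The conclusion rests on four assumptions: two-sided 5%; equal dropout in the arms; the monitoring definition of dropout applied to section 12.6, which gives none of its own; and SD 11.42. That SD describes self-reported adherence levels, not month-to-month changes. The plan gives no SD for change scores, so every figure here inherits the substitution.

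The disagreement within 12.1 between 5.59 points and 0.86 SD (about 9.8 points) is larger than the dropout effect and has to be settled first.

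**What to change.** In section 12.1, in this order:

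1. Reconcile the 90-per-group calculation with the printed 2/30 formula and keep one.
2. Replace the fixed count with up to 180 change scores, about 162–168 at 10% dropout for measures collected at visits, noting that Wisepill scores are lost only when the device is no longer used.
3. Restate the result at 10% dropout from the retained formula. If the 90-per-group version is kept, this is about 75–77% power for 5.59 points, or a detectable difference of about 5.8–5.95 points. If the 2/30 version is kept, it is about 0.90 SD.
4. State alpha and sidedness, and say that the SD is for self-reported adherence levels rather than change scores.

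The dropout restatement itself takes about one sentence. No extra participants, visits or analyses are needed. The only cost is a slightly less favourable stated figure.
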